9.5.3 Analysis of Efficacy Variables

The number and percentage of subjects with at least one biopsy-confirmed or clinically suspected KS lesion that has localized with Tc 99m tilmanocept by planar and/or SPECT/CT imaging will be

computed. A 95% exact confidence interval on the per subject localization rate will be computed. This analysis will be performed by dose.

Per region lesion localization of Tc 99m tilmanocept by planar and/or SPECT/CT imaging will be computed across all biopsy-confirmed or clinically suspected KS lesions of all subjects. A 95% exact confidence interval on per region lesion localization will be calculated. This analysis will be performed by dose.

Localization intensities of biopsied lesions will be summarized by descriptive statistics (mean, median, standard deviation, minimum, maximum and range) for each dose.

Per biopsied lesion proportion of CD206-expressing cells and quantity of CD206 as determined by histology and IHC fluorescence will be summarized by descriptive statistics (mean, median, standard deviation, minimum, maximum and range) for each dose.

Concordance between between IV and SC tilmanocept in biopsy-confirmed or clinically suspected KS lesion sites will be assessed with a cross-tabulation including the joint probability distribution. The site will be the sampling unit for this analysis. An exact version of McNemar's test will be performed, testing the null hypothesis

$$H_0: \pi_{IV} = \pi_{SC}$$

$$H_A: \pi_{IV} \neq \pi_{SC}$$

where π_{IV} and π_{SC} represent the probabilities of localization with IV (only) tilmanocept and localization with SC tilmanocept only respectively.

In addition, descriptive statistics will be generated relative to the concordance and reverse concordance of observed sites of discrete localization of Tc 99m tilmanocept following IV and SC administration.

The number and percentage of subjects with at least one anatomical site other than KS that has been localized with Tc 99m tilmanocept by SPECT imaging will be computed. A 95% exact confidence interval on the per subject localization rate will be computed. This analysis will be performed by dose and overall.

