Appendix 5 KS Lesion Assessment/ Photography Protocol

INTERNATIONAL COLLABORATIVE	Participant ID Number	Interviewer Initials	Date of Visit	Visit Number
	□□□□□□□	□□□	□□/□□□/□□□ □ Day Month Year	□□
	Reviewer Initials	Date of Review	Interim Visit Number	
	□□□	□□/□□□/□□□ □ Day Month Year	□□	

KS LESION ASSESSMENT

A "KS-suspicious" lesion is defined as a lesion that is either known to be KS (by virtue of biopsy) or clinically suspected to be KS. In the questions below, when asked about KS-suspicious lesions, consider only those which are **hyperpigmented** with the usual characteristics of KS, regardless if they are flat or raised. Do not count lesions which have subcutaneous swelling alone, without hyperpigmentation, as KS-suspicious.

A. Overall Cutaneous Do not count oral cavity lesions.

1. Overall inventory: How many KS-suspicious lesions are present? 1-49 ≥ 50

2. Indicate if KS-suspicious lesions are absent or present in each of these sites.

Site #	Absent	Present	Site #	Absent	Present	Site #	Absent	Present
12 – Head			17 – Right arm			22 – Left hand		
13 – Neck			18 – Left arm			23 – Right foot		
14 – Chest			19 – Right leg			24 – Left foot		
15 – Abdomen			20 – Left leg			25 – Genital		
16 – Back			21 – Right hand			26 – Gluteal		

Lesion Counts

Include only KS-suspicious lesions (do not include lesions with subcutaneous swelling alone).

If ≥ 50 lesions overall, select three sites that are **most representative** of the total body in terms of lesion characteristics and which have a combined lesion count of at least 50. If three such areas cannot be found which total at least 50 lesions, choose 3 areas with the largest combined count. Indicate the sites using the corresponding codes above. Do not use the mouth. If lesions are only present in the mouth, go to question 4.

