4.0 Analysis of Efficacy

4.1 Description of Efficacy Variables

Secondary objectives of the study are to determine the concordance between clinical assessment/diagnosis and the localization of Tc 99m tilmanocept by planar and/or SPECT/CT imaging in cutaneous and non-cutaneous sites of KS; to qualify and quantify Tc 99m tilmanocept localization intensity on imaging with CD 206 locale and quantity by histology and IHC in biopsied KS lesions to determine the optimal IV dose; and concordance of localization of Tc 99m tilmanocept via IV and SC routes of administration by planar and/or SPECT/CT imaging in cutaneous and non-cutaneous sites of KS. The relevant endpoints are the following:

- Per subject localization rate of Tc 99m tilmanocept in at least one KS suspected or confirmed lesion by planar and/or SPECT/CT imaging
- Per lesion/region concordance of Tc 99m localization with anatomical areas of active KS defined by confirmed diagnosis or clinical symptomology

- Localization intensity for each biopsied and clinically defined lesion localized on imaging following IV injection as determined by quantitative SPECT gamma counts
- Per biopsied lesion proportion of CD206-expressing cells and proportion of HHV8-expressing cells as determined by histology and relative IHC fluorescence
- Per lesion/region concordance of IV vs SC Tc 99m localization with anatomical areas of active KS defined by confirmed diagnosis or clinical symptomology.
- Per subject localization rate of Tc 99m tilmanocept in areas other than KS by planar and/or SPECT/CT imaging
- Per area localization rate of Tc 99m tilmanocept in the most frequently identified areas other than KS by planar and/or SPECT/CT imaging

An exploratory objective of the study is to use quantitative Polymerase Chain Reaction (qPCR) methods to measure the amount of Human Herpes Virus 8 (HHV8) present in the biopsy tissue.

The relevant variables are the following:

- Nuclear medicine specialist determination of presence/absence of illumination (i.e., localization positive or negative per anatomic site) relative to background from planar and/or SPECT/CT imaging results for each subject;
- Clinically identified presence or absence of KS based on any previous diagnostic evaluation;
- Proportion of CD206-expressing cells (IHC fluorescence);
- Quantitative SPECT gamma counts for each biopsied lesion localized on imaging following IV injection; and,
- HHV8 concentrations as determined by qPCR for each biopsied lesion.

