4.2 Analysis of Efficacy Variables

Localization in KS Sites

The number and percentage of subjects with at least one biopsy-confirmed or clinically suspected KS lesion that has localized with Tc 99m tilmanocept by planar and/or SPECT/CT imaging will be computed. A 95% exact confidence interval on the per-subject localization rate will be computed. This analysis will be performed by dose group and route of administration.

Per-lesion/region localization of Tc 99m tilmanocept by planar and/or SPECT/CT imaging will be computed across all biopsy-confirmed or clinically suspected KS lesions of all subjects. A 95% exact confidence interval on the per-lesion/region localization will be calculated. This analysis will be performed by dose group and route of administration.

An analysis table will also be provided to display the counts of KS lesions localized by imaging that were not previously identified clinically.

Concordance between IV and SC tilmanocept in biopsy-confirmed or clinically-suspected KS lesion sites will be assessed with a cross-tabulation of the IV and SC findings, including the joint probability distribution. The sampling unit for this analysis will be the site. An exact conditional version of McNemar's test will be performed to test the hypotheses

$$H_0: \pi_{IV} = \pi_{SC}$$
$$H_A: \pi_{IV} \neq \pi_{SC},$$

where π_{IV} and π_{SC} represent the probabilities of localization with IV (only) tilmanocept and SC (only) tilmanocept, respectively. In addition, the number and proportion of subjects with concordance and reverse concordance of observed sites of discrete localization of Tc 99m tilmanocept following IV and SC localization will be summarized.

Localization Intensity by Planar and/or SPECT/CT Imaging

Tc 99m tilmanocept average pixel intensity and percent above background will be summarized with descriptive statistics (mean, standard deviation, minimum, median, maximum, and range) for each biopsied lesion localized on imaging following IV injection of Tc 99m tilmanocept by dose group. Summary statistics will be presented separately by imaging type (planar, SPECT/CT).

Proportion of CD206-expressing Cells

Per biopsied-lesion proportion of CD206-expressing cells as determined by histology and IHC fluorescence will be summarized by descriptive statistics (mean, standard deviation, minimum, median, maximum, and range) by dose group.

Localization in Non-KS Sites

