	Female	xxx (xxx%)	xxx (xxx%)	xxx (xxx%)	xxx (xxx%)
Race	American Indian or Alaska Native	xxx (xxx%)	xxx (xxx%)	xxx (xxx%)	xxx (xxx%)
	Asian	xxx (xxx%)	xxx (xxx%)	xxx (xxx%)	xxx (xxx%)
Race	Black or African American	xxx (xxx%)	xxx (xxx%)	xxx (xxx%)	xxx (xxx%)
	Native Hawaiian or Other Pacific Islander	xxx (xxx%)	xxx (xxx%)	xxx (xxx%)	xxx (xxx%)
Race	White	xxx (xxx%)	xxx (xxx%)	xxx (xxx%)	xxx (xxx%)
	Other	xxx (xxx%)	xxx (xxx%)	xxx (xxx%)	xxx (xxx%)
Ethnicity	Hispanic or Latino	xxx (xxx%)	xxx (xxx%)	xxx (xxx%)	xxx (xxx%)
	Not Hispanic or Latino	xxx (xxx%)	xxx (xxx%)	xxx (xxx%)	xxx (xxx%)

Cohort 1 = 100µg/5mCi IV; Cohort 2 = 100µg/10mCi IV; Cohort 3 = 200µg/5mCi IV and SC.
 STAKING Clinical Services (DD-MMM-YYYY)
 Source Program: xxxxxxxx.sas

Page x of y

Table 4. Summary of Study Drug Administration by Cohort
 Navidea Biopharmaceuticals - Study No. NAV3-24
 Safety Population (N=xxx)

	Group	Mean	Std Dev	n	Min	Max	Median
Tc 99m Dose (mCi)	Cohort 1 IV	xxxx	xxxx	xx	xxxx	xxxx	xxxx
	Cohort 2 IV	xxxx	xxxx	xx	xxxx	xxxx	xxxx
	Cohort 3 IV	xxxx	xxxx	xx	xxxx	xxxx	xxxx
	Cohort 3 SC	xxxx	xxxx	xx	xxxx	xxxx	xxxx
Mass Dose (µg)	Cohort 1 IV	xxxx	xxxx	xx	xxxx	xxxx	xxxx
	Cohort 2 IV	xxxx	xxxx	xx	xxxx	xxxx	xxxx
	Cohort 3 IV	xxxx	xxxx	xx	xxxx	xxxx	xxxx
	Cohort 3 SC	xxxx	xxxx	xx	xxxx	xxxx	xxxx

Cohort 1 = 100µg/5mCi IV; Cohort 2 = 100µg/10mCi IV; Cohort 3 = 200µg/5mCi IV and SC.

STATKING Clinical Services (DD-MMM-YYYY)

Source Program: xxxxxxxx.sas

Table 5. Subject-Level Localization of KS Lesions-Nuclear Medicine Findings
 Navidea Biopharmaceuticals - Study No. NAV3-24
 ITD Population (N=xxx)

Group	Number of Subjects	Number (Proportion) Localized	95% Exact One-Sided Binomial CI for Proportion
Cohort 1 IV	xx	xxx (xxx)	(xxx, xxx)
Cohort 2 IV	xx	xxx (xxx)	(xxx, xxx)
Cohort 3 IV	xx	xxx (xxx)	(xxx, xxx)
Cohort 3 SC	xx	xxx (xxx)	(xxx, xxx)
All Cohorts Combined	xx	xxx (xxx)	(xxx, xxx)

Cohort 1 = 100 μ g/5mCi IV; Cohort 2 = 100 μ g/10mCi IV; Cohort 3 = 200 μ g/5mCi IV and SC.
 STATKING Clinical Services (DD-MMM-YYYY)
 Source Program: xxxxxxxx.sas

Table 6. Lesion-Level Localization of KS Lesions-Nuclear Medicine Findings
 Navidea Biopharmaceuticals - Study No. NAV3-24
 ITD Population (N=xxx)

Group	Number of Clinically Identified Lesions ^a	Number (Proportion) Localized by Imaging	95% Exact One-Sided Binomial CI for Proportion
Cohort 1 IV	xx	xxx (xxx)	(xxx, xxx)
Cohort 2 IV	xx	xxx (xxx)	(xxx, xxx)
Cohort 3 IV	xx	xxx (xxx)	(xxx, xxx)
Cohort 3 SC	xx	xxx (xxx)	(xxx, xxx)

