All Cohorts Combined	xx	xxx (xxx)	(xxx, xxx)

^a Number of cutaneous and non-cutaneous lesions identified in screening.

Cohort 1 = 100 μ g/5mCi IV; Cohort 2 = 100 μ g/10mCi IV; Cohort 3 = 200 μ g/5mCi IV and SC.

STATKING Clinical Services (DD-MMM-YYYY)

Source Program: xxxxxxx.sas

Page x of y

Table 7. Additional KS Lesions Identified from Imaging That Were Not Seen Clinically - Nuclear
Medicine Findings
Navidea Biopharmaceuticals - Study No. NAV3-24
ITD Population (N=xxx)

Group	Number of Identified Lesions	Number (Proportion) of Subjects with at Least 1 Identified Lesion
Cohort 1 IV	xx	xxx (xxx)
Cohort 2 IV	xx	xxx (xxx)
Cohort 3 IV	xx	xxx (xxx)
Cohort 3 SC	xx	xxx (xxx)
All Cohorts Combined	xx	xxx (xxx)

Cohort 1 = 100 μ g/5mCi IV; Cohort 2 = 100 μ g/10mCi IV; Cohort 3 = 200 μ g/5mCi IV and SC.
STATKING Clinical Services (DD-MMM-YYYY)
Source Program: xxxxxxxx.sas

Table 8. Lesion-level Non-Localization of KS Lesions - Nuclear Medicine Findings
 Navidea Biopharmaceuticals - Study No. NAV3-24
 ITD Population (N=xxx)

Group	Number of Clinically Identified Lesions ^a	Number (Proportion) Not Localized by Imaging	95% Exact One-Sided Binomial CI for Proportion
Cohort 1 IV	xx	xxx (xxx)	(xxx, xxx)
Cohort 2 IV	xx	xxx (xxx)	(xxx, xxx)
Cohort 3 IV	xx	xxx (xxx)	(xxx, xxx)
Cohort 3 SC	xx	xxx (xxx)	(xxx, xxx)
All Cohorts Combined	xx	xxx (xxx)	(xxx, xxx)

^a Number of cutaneous and non-cutaneous lesions identified in screening.
 Cohort 1 = 100 μ g/5mCi IV; Cohort 2 = 100 μ g/10mCi IV; Cohort 3 = 200 μ g/5mCi IV and SC.
 STATKING Clinical Services (DD-MMM-YYYY)
 Source Program: xxxxxxxx.sas

Page x of y

Table 9. Number and Percentage of Concordant and Reverse Concordant Lesions
Navidea Biopharmaceuticals - Study No. NAV3-24
ITD Population (N=xxx)

IV Result	SC Result		Total	Concordance	Reverse Concordance	p-Value (McNemar's Test)
	Localized	Not Localized				
Localized	xx (xxx%)	xx (xxx%)	xx (xxx%)	xxx (xxx%)	xxx (xxx%)	xxx
Not Localized	xx (xxx%)	xx (xxx%)	xx (xxx%)			
Total	xx (xxx%)	xx (xxx%)				

STATKING Clinical Services (DD-MMM-YYYY)
Source Program: xxxxxxxx.sas

Page x of y

Table 10. Summary of Imaging-Localized Biopsied Lesion Localization Intensity by Cohort -
 Imaging = Planar
 Navidea Biopharmaceuticals - Study No. NAV3-24
 ITD Population (N=xxxx)

Group	Variable ^a	Mean	Std Dev	n	Min	Max	Median
Cohort 2 IV	Avg Pixel Intensity Percent Above Background	xx xx	xx xx	xx xx	xx xx	xx xx	xx xx

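### The IV versus SC McNemar test is specified per site, but its table shell counts lesions: define both units and report Table 9 per site

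*SAP*

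**What the plan says.** The unit of observation changes from place to place.

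- **IV/SC test.** SAP 4.2: "The sampling unit for this analysis will be the site". Protocol 9.5.3 sets the same unit.
- **Shell for that test.** Table 9 in SAP Appendix B: "Number and Percentage of Concordant and Reverse Concordant Lesions".
- **Concordance summary.** The sentence in SAP 4.2 that follows the test counts subjects.
- **Reader variable.** SAP 4.1: "localization positive or negative per anatomic site". Protocol 9.3 names a result and an anatomic site side by side, without saying that there is one result per site.
- **Reader data.** Data Listing 18 has a lesion column next to the reader's visualization. SAP 1.1.1 defines a localized KS lesion, so at lesion level.
- **Localization endpoint.** SAP 4.1: "Per lesion/region concordance of Tc 99m localization with anatomical areas of active KS". SAP 4.2: "Per-lesion/region localization of Tc 99m tilmanocept by planar and/or SPECT/CT imaging will be computed across all biopsy-confirmed or clinically suspected KS lesions". Protocol 9.5.3: "Per region lesion localization of Tc 99m tilmanocept by planar and/or SPECT/CT imaging".
- **Shells for that endpoint.** Tables 6 and 8 divide by "Number of Clinically Identified Lesions".
- **Clinical form.** Protocol Appendix 5 uses site for a coded body region ("Indicate if KS-suspicious lesions are absent or present in each of these sites") and counts lesions within sites.

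Neither document defines lesion, region and site relative to each other, or says how a result for a site relates to the lesions in it.

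**The concern.** A programmer who follows the SAP text builds the IV/SC cross-tabulation from sites. One who follows the Table 9 shell builds it from lesions. The two can give different p-values from the same scans.

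The difference is not neutral. Lesions in the same body region may well light up, or fail to, together. Each of them then enters Table 9 as if it were separate evidence, and a region with many lesions carries more weight than one with a single lesion. Only Cohort 3, up to 6 subjects, supplies this comparison, so a few heavily affected regions could carry much of it.

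For Tables 6 and 8 the issue is the estimate itself. A rate per lesion and a rate per region answer different questions, and the words lesion/region do not choose between them. If the choice is left open, it can be made after the results are known.

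**Working it through.** **The plan's own figures.** The planned size is 4 + 4 + up to 6 = up to 14 subjects, which reproduces. The documents give no expected number of lesions or sites, and no alpha for the McNemar test. All lesion counts below are therefore assumptions, and 0.05 two-sided is assumed where a threshold is used. Appendix 5 has 15 cutaneous site codes (12 to 26) and records the overall lesion count as 1-49 or as 50 and more. The assumed counts per region stay within the lower band.

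**IV/SC test.** Let b be the units localized by IV only and c those localized by SC only. The exact conditional test gives p = min(1, 2 × P(X ≥ max(b, c))), with X ~ Binomial(b + c, ½).

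Take one region localized by IV only and no other discordance (c = 0):

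| Counted as | b | p |
|---|---|---|
| one site | 1 | min(1, 2 × 0.5) = 1.00 |
| 5 lesions | 5 | 2 × 0.5^5 = 0.0625 |
| 6 lesions | 6 | 2 × 0.5^6 = 0.031 |
| 10 lesions | 10 | 2 × 0.5^10 = 0.002 |

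Now add single-lesion sites that point the other way:

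- 10 lesions in one IV-only region against 2 SC-only sites: 10 v 2 gives p = 0.039 per lesion; 1 v 2 gives p = 1.00 per site.
- 15 lesions against 5 SC-only sites: 15 v 5 gives p = 0.041 per lesion; 1 v 5 gives p = 0.22 per site.

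**Type I error.** A simulation with 40,000 runs per setting assumed no IV/SC difference, 12 to 24 independent sites, 20% to 40% of sites discordant, equal lesion numbers per site, and one shared result for all lesions in a site. Full sharing is the extreme case.

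| Unit | Rejection rate |
|---|---|
| site | at most about 2.4% |
| lesion, 2 per site | 8-13% |
| lesion, 3 per site | 23-25% |
| lesion, 6 per site | 38-52% |
| lesion, 10 per site | 50-54% |

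**Localization rate.** Take one localized region holding m lesions and five single-lesion regions not localized. Per site the rate is 1/6 = 16.7%. Per lesion it is m/(m + 5): 6/11 = 54.5%, 20/25 = 80.0% and 49/54 = 90.7% for m = 6, 20 and 49. Reverse the results and the shift reverses: 5/6 = 83.3% per site, against 5/11 = 45.5% per lesion for m = 6 and 5/25 = 20.0% for m = 20. So lesion counting can move the rate either way.

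**The case against.** The strongest defence is that site here means the place of a lesion. SAP 4.2 introduces the test with the phrase KS lesion sites, so Table 9 would agree with the text. That reading is possible. It is not the SAP's consistent usage: SAP 4.1 speaks of the anatomic site, and the shells separate lesion-level results (Tables 6 and 8) from site-level results by anatomical site (Table 15).

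A reader might infer that the physician makes one call per body region and that it will be copied to every lesion there. The documents do not support this. Data Listing 18 shows visualization by lesion, SAP 1.1.1 defines localization for a lesion, and only SAP 4.1 says per anatomic site. Separate calls for every lesion cannot be taken for granted either, since planar imaging is the required scan and SPECT/CT is optional.

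A reader might also infer that the plan already adopts the Appendix 5 body codes. It does not. SAP 4.2 never cites that form, and its site codes cover neither the oral cavity nor internal organs.

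It can fairly be added that the p-value effect is replication within regions, a form of clustering, and that moving to sites does not remove correlation within a subject. SAP 2.1 describes all results as descriptive, and no decision rests on Table 9. These points stand and limit the weight of the finding. They do not remove the mismatch between the test's stated unit and its table.

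**Conclusion.** The inconsistency is in the text: both documents set the site as unit of the IV/SC McNemar test, and the only shell reporting it counts lesions. Tables 6 and 8 settle on lesions for an endpoint whose wording leaves the unit open.

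The size depends on two things the documents do not give: how many lesions share a region, and how strongly their results agree. Under full agreement, one discordant region moves from p = 1.00 to p = 0.031 with 6 lesions. With weaker agreement the effect is smaller. It would go too far to say that one region will decide the rate or the p-value in this trial.

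The finding concerns secondary endpoints. The primary adverse drug reaction endpoint and the per-subject localization rate (Table 5) are counted by subject and do not change. The correction should be made before analysis.

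**What to change.** 1. In SAP 1.1.1, define lesion and anatomic site, with a fixed site list. One option is the Appendix 5 codes plus the oral cavity and each non-cutaneous organ.
2. Run and title Table 9 per site, as the SAP text states. Set one rule in advance for sites with mixed findings, for example that a site is localized if at least one clinically identified lesion in it is illuminated. State its limit: under that rule a site with 1 of 40 lesions illuminated counts as localized.
3. Keep Tables 6 and 8 per lesion, with every clinically identified lesion in the denominator, including those not resolved on the scan. Add a labelled per-site row. For subjects with 50 or more lesions, name the source of the count: Protocol 7.1 asks for all cutaneous lesions to be documented, but the Appendix 5 count covers three representative sites.
4. State that a site-level call is not copied to every lesion in the site.
5. Label the McNemar p-value descriptive, because sites within at most 6 Cohort 3 subjects remain correlated.

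The cost is SAP wording, a retitled Table 9 and extra rows in Tables 6 and 8. Site-level numbers are smaller and their intervals wider: in the rate example, 1/6 has a two-sided exact 95% interval of 0.4% to 64.1%, against 59.3% to 93.2% for 20/25.

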Dose(s) and Route of Administration	
Route of Administration: Administrations of Tc 99m tilmanocept will occur through an intravenous (IV) and subcutaneous (SC) route of injection.
 
For the IV doses, a single syringe will be used and injected as a slow push into the peripheral venous catheter. The preferred site of catheter placement will be the left or right antecubital vein. At the completion of the injection, a 10 cc sterile normal saline flush will be administered.
 
For SC doses, two syringes will be used and injected bilaterally as a slow push into the ankle(s) or the dorsal surface of the foot (feet).
 
Doses: Cohort 1 subjects will receive an IV administration of 100 µg/ 5 mCi Tc 99m tilmanocept. Cohort 2 subjects will receive an IV administration of 100 µg/ 10 mCi Tc 99m tilmanocept. Cohort 3 subjects will receive a SC and an IV administration of 200 µg/ 5 mCi Tc 99m tilmanocept approximately one week apart.

Study Objectives	
Primary Objective(s):
 
To determine the safety of escalating doses of Tc 99m tilmanocept in HIV subjects with biopsy-confirmed KS.
 
Secondary Objective(s):
 
Concordance between clinical assessment/diagnosis and the localization of Tc 99m tilmanocept by planar and/or SPECT (single photon emission computed tomography)/CT (X-ray computed tomography) imaging in cutaneous and non-cutaneous sites of KS.Qualify and quantify Tc 99m tilmanocept localization intensity on imaging with CD206 locale and quantity by histology and immunohistochemistry (IHC) in biopsied KS lesions to determine optimal IV dose.Concordance of localization of Tc 99m tilmanocept via IV and SC routes of administration by planar and/or SPECT/CT imaging in cutaneous and non-cutaneous sites of KS. 
Exploratory Objective(s):

	
Quantify HHV8 in biopsied KS lesions by real-time polymerase chain reaction (qPCR) 
Safety:
 
General safety will be evaluated by examining the incidence of adverse events (AEs) and changes over time in laboratory tests, vital signs, ECGs (electrocardiogram) and physical examination findings.

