8.3 SPECT/SPECT-CT Image Acquisition

The camera used to obtain the images should be a 2-headed SPECT or SPECT/CT camera equipped with a low-energy, high-resolution collimator with a 15% window (20% can be used if 15% setting not available) centered over a 140keV peak.

The camera must have passed the daily SPECT QC (quality control) tests as per the manufacturer's recommendation for that day's scan schedule.

Whenever possible, subject should be asked to void after injection and prior to the imaging session.

Subjects should be positioned supine with arms at their side. The subject's head, legs, hands, and hips should be in the true anterior position. The subject should be instructed to remain as motionless as possible during the scan and asked to breathe as shallowly as comfortable when the camera is passing over the chest. To help minimize leg motion, a light tape around the ankles can be used to keep the legs together. A pillow under the knees is often very helpful for comfort.

A whole body planar scan should be obtained at the following time points:

- 60-75 minutes post-IV/SC administration
- 4-6 hours post-SC injection

Optional SPECT/CT region(s) of interest scan(s) can be obtained at the following time points:

- 60-75 minutes post-IV/SC administration
- 4-6 hours post-SC injection

It is anticipated that the whole body planar scan would be acquired first for 25-30 minutes. Using a 2-headed camera (nominal 20" x 15" FOV [field of view]) a target of 5-7 million counts should be obtained for the summed view of both heads. For the higher activity injections, it may be possible to attain this target in a shorter time, allowing the subject more time off the bed between scans.

Following the whole body scan, optional SPECT/CT region(s) of interest scan(s) can be obtained. It is anticipated that a SPECT/CT scan would be acquired over 25-30 minutes. The use of a calibration syringe for each SPECT scan is not necessary. It is very important that the subject remain motionless for the duration of the complete SPECT/CT scan.

SPECT/CT slices will be reconstructed using the manufacturer's recommended reconstruction algorithms including the recommended attenuation correction.

It is strongly recommended that each site should perform all imaging acquisitions per their camera manufacturer and model parameters and in accordance with their institutional practices for both the whole body scan as well as the SPECT/CT imaging.

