9.3 Efficacy Variables

The efficacy variables for this study are as follows:

- Nuclear medicine specialist determination of presence/absence of illumination (i.e., localization positive/negative, anatomic site) relative to background from SPECT imaging results for each subject;
- Clinically identified presence/absence of KS (based on any previous diagnostic evaluations);
- Quantitative SPECT gamma counts for each biopsied lesion.

The efficacy endpoints for this study are as follows:

- Per subject localization rate of Tc 99m tilmanocept in at least one KS suspected or confirmed lesion by planar and/or SPECT/CT imaging
- Per lesion/region concordance of Tc 99m localization with anatomical areas of active KS defined by confirmed diagnosis or clinical symptomology
- Localization intensity for each biopsied and clinically defined lesion as determined by quantitative SPECT gamma counts
- Per biopsied lesion proportion of CD206-expressing cells and total CD206 as determined by histology and relative IHC fluorescence
- Per lesion/region concordance of IV vs SC Tc 99m localization with anatomical areas of active KS defined by confirmed diagnosis or clinical symptomology.
- Per subject localization rate of Tc 99m tilmanocept in areas other than KS by planar and/or SPECT/CT imaging

- Per area localization rate of Tc 99m tilmanocept in the most frequently identified areas other than KS by planar and/or SPECT/CT imaging

A localized subject is one for whom Tc 99m by planar and/or SPECT/CT imaging results in the illumination of at least one site relative to background as determined by the nuclear medicine specialist.

A localized KS lesion is a lesion that is both clinically identified or suspected KS and planar or SPECT/CT illuminated.

Localization in areas other than KS will also be defined per subject and per area, where these areas are clinically negative KS locations based on clinical symptomology.

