				CNS/Neurological	xxxxxx	xxxxxxxxxxxxxxxxxxxxxxxxxxxxxx

Cohort 1 = 100 μ g/5mCi IV; Cohort 2 = 100 μ g/10mCi IV; Cohort 3 = 200 μ g/5mCi IV and SC.

STATKING Clinical Services (DD-MMM-YYYY)

Source Program: xxxxxxxx.sas

Data Listing 14. Vital Signs Data Listing
Navidea Biopharmaceuticals - Study No. NAV3-24
Safety Population (N=xxx)

Cohort	Subject No.	Visit/ Date	Time	Temperature (°F)		Systolic Blood Pressure (mmHg)		Diastolic Blood Pressure (mmHg)		Heart Rate (bpm)		Respirations per Minute	
				Value	Normal (Y/N)	Value	Normal (Y/N)	Value	Normal (Y/N)	Value	Normal (Y/N)	Value	Normal (Y/N)
xxxxxx	xxxx	xxxxxxxx/xxxxxx	xxxxx	xxx	x	xxx	x	xxx	x	xxx	x	xxx	x
			xxxxx	xxx	x	xxx	x	xxx	x	xxx	x	xxx	x
			xxxxx	xxx	x	xxx	x	xxx	x	xxx	x	xxx	x
xxxxxx	xxxx	xxxxxxxx/xxxxxx	xxxxx	xxx	x	xxx	x	xxx	x	xxx	x	xxx	x
			xxxxx	xxx	x	xxx	x	xxx	x	xxx	x	xxx	x
			xxxxx	xxx	x	xxx	x	xxx	x	xxx	x	xxx	x

Cohort 1 = 100µg/5mCi IV; Cohort 2 = 100µg/10mCi IV; Cohort 3 = 200µg/5mCi IV and SC.

STATKING Clinical Services (DD-MMM-YYYY)

Source Program: xxxxxxx.sas

Page x of y

Data Listing 15. Study Drug Administration Data Listing
Navidea Biopharmaceuticals - Study No. NAV3-24
Safety Population (N=xxx)

Cohort	Subject No.	Date/ Time of Injection	Anatomic Location of Injection	Pre-Injection Radioactivity (mCi)/Time of Measurement	Post- Injection Radioactivity (mCi)/Time of Measurement	Calculated Amount of Administered Radioactivity (mCi)	Calculated Mass Dose (μ g)	Lot Number
xxxxxx	xxxx	xxxxxx/xxxx	xxxxxxx	xxx/ xxxx	xxx/ xxxx	xxx	xxx	xxx
xxxxxx	xxxx	xxxxxx/xxxx	xxxxxxx	xxx/ xxxx	xxx/ xxxx	xxx	xxx	xxx

Cohort 1 = 100 μ g/5mCi IV; Cohort 2 = 100 μ g/10mCi IV; Cohort 3 = 200 μ g/5mCi IV and SC.

STATKING Clinical Services (DD-MMM-YYYY)

Source Program: xxxxxxx.sas

Page x of y

Data Listing 16. Post-Injection Imaging Data Listing
Navidea Biopharmaceuticals - Study No. NAV3-24
ITD Population (N=xxx)

Cohort	Subject No.	Date of Imaging	Start Time of Planar Imaging	SPECT/CT Imaging Start Time
xxxxxx	xxxx	xxxxxx	xx:xx	xx:xx
xxxxxx	xxxx	xxxxxx	xx:xx	xx:xx

Cohort 1 = 100 μ g/5mCi IV; Cohort 2 = 100 μ g/10mCi IV; Cohort 3 = 200 μ g/5mCi IV and SC.
STATKING Clinical Services (DD-MMM-YYYY)
Source Program: xxxxxxxx.sas

Page x of y

Data Listing 17. Quantitative Imaging Results Data Listing
Navidea Biopharmaceuticals - Study No. NAV3-24
ITD Population (N=xxx)

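### Average pixel intensity is summarised by dose group and pooled with no stated adjustment for injected activity or scan time, so that measure cannot separate lesion uptake from activity

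*SAP*

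**What the plan says.** **Purpose and endpoint.** A secondary objective (Protocol 2.2, SAP 4.1) ties localization intensity to finding the optimal IV dose. Protocol 9.3 gives the endpoint as "Localization intensity for each biopsied and clinically defined lesion as determined by quantitative SPECT gamma counts".

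**Analysis.** SAP 4.2 says that "Tc 99m tilmanocept average pixel intensity and percent above background will be summarized with descriptive statistics". It covers biopsied lesions that localised after IV injection, by dose group and split by image type. SAP 2.1 makes all results descriptive.

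**Doses.** The protocol synopsis says "Cohort 1 subjects will receive an IV administration of 100 µg/ 5 mCi Tc 99m tilmanocept" and "Cohort 2 subjects will receive an IV administration of 100 µg/ 10 mCi Tc 99m tilmanocept". Cohort 3 receives 200 µg/5 mCi IV (Protocol Table 1).

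**Acquisition (Protocol 8.3).** The whole body planar scan is expected to take 25 to 30 minutes, with a target of 5 to 7 million counts, and "For the higher activity injections, it may be possible to attain this target in a shorter time". The optional SPECT/CT scan is also expected to take 25 to 30 minutes but has no count target. The protocol adds: "The use of a calibration syringe for each SPECT scan is not necessary".

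**Tables and listings (SAP Appendix B).** The shells for Tables 10 and 11 have rows for Cohort 2 IV, Cohort 3 IV and all cohorts combined, each with both intensity measures. There is no Cohort 1 row, although the footnote defines Cohort 1. Data Listing 15 records administered activity, Data Listing 16 records scan start times only, and Data Listing 17 records lesion intensity, background intensity and percent above background.

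**The concern.** The counts in a pixel depend on how much of the injected tracer reaches the lesion, how much activity was injected, and how long the camera collected. Only the first describes lesion uptake. The IV dose groups differ twofold in activity, scan time is not fixed, and neither document says that average pixel intensity is divided by either.

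A higher mean in Cohort 2 could therefore reflect activity or scan length alone. The reverse can also happen. At equal scan time, Cohort 3 lesions with twice the fractional uptake would match Cohort 2 on this measure (2 × 5 mCi = 1 × 10 mCi), hiding a real difference. The summary feeds the optimal-dose objective, and the pooled row averages values that are not on a common scale.

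**Working it through.** The documents give no figure for an intensity ratio, so there is none to reproduce. The check asks what the plan would show if lesion uptake were identical in every cohort.

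**Inputs.** Activity 5, 10 and 5 mCi (Protocol Table 1); scan time 25 to 30 minutes for either image type, and a planar target of 5 to 7 million counts (Protocol 8.3); cohort sizes 4, 4 and up to 6 (Protocol Table 1).

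**Model (assumed).** Pixel counts ∝ uptake fraction × injected mCi × minutes, with a linear detector and the same uptake fraction throughout.

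**1. Time-based scans, 10 mCi against 5 mCi.** This fits SPECT/CT most directly.
- Equal time: 10/5 = 2.00.
- Smallest ratio: (10 × 25)/(5 × 30) = 250/150 = 1.67.
- Largest ratio: (10 × 30)/(5 × 25) = 300/125 = 2.40.

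**2. Planar scans stopped at the count target.**
- Same total counts: 1.00.
- Anywhere within the target: 5/7 = 0.71 to 7/5 = 1.40.
- Time Cohort 2 would need to match the 5 mCi counts: 25 × 5/10 = 12.5 to 30 × 5/10 = 15 minutes.

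The shorter scan is permitted, not required. The actual planar ratio is therefore unknown without recorded scan durations.

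**3. Percent above background.** Taking this as 100 × (lesion − background)/background, which fits the columns of Data Listing 17, activity and time cancel. With an assumed lesion-to-background ratio of 3:1:
- 5 mCi: 100 × (15 − 5)/5 = 200%.
- 10 mCi: 100 × (30 − 10)/10 = 200%.

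**4. Pooled row at equal scan time.** Set the 5 mCi value to 1 and the 10 mCi value to 2, and assume every planned subject contributes a localised biopsied lesion.

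| Cohorts pooled | Mean | SD | CV |
|---|---|---|---|
| 2 and 3 | (4 × 2 + 6 × 1)/10 = 1.40 | 0.52 | 37% |
| 1, 2 and 3 | (4 × 1 + 4 × 2 + 6 × 1)/14 = 1.29 | 0.47 | 36% |

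All of that spread comes from injected activity and none from uptake.

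**5. After normalising.** Dividing counts by administered mCi and minutes gives a ratio of 1.00 at identical uptake, whatever the scan time.

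**6. Decay.** The 15-minute width of the 60 to 75 minute start window adds little: 1 − 0.5^(15/361) = 2.8%, assuming a half-life of about 6 hours (361 minutes).

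**The case against.** The best defence is that SAP 4.2 already plans a measure free of the problem. Percent above background is named in the same sentence, and Data Listing 17 lists the background value for each lesion. This stands. A reader might infer that the plan has no valid intensity comparison across doses, and the documents do not support that. What is missing is a statement of which measure carries the cross-dose reading.

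Second, a reader might infer that Cohort 2 will look twice as bright. Twofold needs equal scan time, and the planar count target could bring the ratio near 1. That relief is for planar only; SPECT/CT, the modality named in the protocol endpoint, has no such target.

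Third, a reader might take the endpoint to be raw counts. Neither document uses that word or defines how pixel intensity is derived. The supportable statement is that normalisation is not specified.

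Fourth, the analysis is secondary and descriptive, in small cohorts with optional SPECT/CT. No rule selects a dose from intensity, and escalation depends on adverse drug reactions (Protocol 5.3). This limits the consequence, but the summaries are still the intensity evidence for the optimal-dose objective.

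Fifth, activity is part of the dose under study, and Cohorts 1 and 2 differ in nothing else. A per-mCi value removes the effect of activity on the image by design. That is a good reason to add it beside the existing measure and not to substitute it.

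**Conclusion.** The point holds for one of the two planned measures. As specified, average pixel intensity mixes uptake with injected activity and scan duration. The size is about twofold for time-based scans, most directly SPECT/CT, and anywhere from 0.71 to 2.40 for planar scans depending on when they are stopped. These ratios assume identical fractional uptake and a linear detector. They are what the plan allows, not a prediction of the results.

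The pooled row for this measure is not interpretable. The shells add a separate gap: without Cohort 1, the displayed contrast is Cohort 2 against Cohort 3, which also differ in mass (100 against 200 µg). Normalising for activity does not remove that difference. The contrast that isolates activity, Cohort 1 against Cohort 2, is not shown although SAP 4.2 promises results by dose group.

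**What to change.** In SAP 4.2 and Tables 10 and 11:

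- Name percent above background as the measure for comparing intensity across doses, and state its formula.
- Keep average pixel intensity, define how it is derived, and add counts per pixel per second per administered mCi, with the administered activity decay-corrected to scan start.
- Take administered activity from Data Listing 15. Take scan duration from the DICOM files that Protocol 7.9 and 8.3 already send to the sponsor, and add it to Data Listing 16. The documents do not confirm that usable durations can be read from these files; if they cannot, site records would be needed.
- Add the Cohort 1 row, or explain its absence.
- Remove unadjusted average pixel intensity from the combined row.

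The cost is a little programming and one extra data field for scan duration. No subject procedure, dose or imaging schedule changes.
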